## 9. Statistical Analysis

## 9.1 Analysis Set

Statistical analysis is performed using full analysis set (FAS), per-protocol set (PPS) and safety set (SS).

FAS: it includes all subjects who have received at least one dose of the investigational drug and have measurable tumors at baseline.

PPS: it includes subjects with at least one post-treatment imaging assessment of tumors, good compliance, and no serious violation or deviation against the study protocol in FAS population.

SS: it includes subjects who have received at least one dose of the investigational drug and undergone safety assessment.

## 9.2 Sample Size Determination

During Phase I monotherapy dose escalation study, the starting dose group (MGD013 120 mg Q2W) will adopt single-subject dose escalation and one subject will be enrolled. Subsequent dose groups and combination treatment will adopt the traditional 3+3 dose escalation scheme, with 3 - 6 evaluable subjects each, 30 - 43 subjects in total.

Phase II Part 1 is a single-arm, SWOG two-stage design study with ORR as its primary efficacy endpoint.

40 subjects are needed
There are 2 stages for the 2nd line cohort and the radiological response (according to RECIST1.1 criteria) of 3 and more out of 20 evaluable subjects at the first stage will support the decision to proceed to the second stage of subject accrual until there are 40 evaluable subjects in this cohort.

Assuming the dropout rate is 10%, 34 subjects will be enrolled.

Similarly, the study has two stages. In the first stage, if response (according to RECIST 1.1 criteria) is observed radiologically in 1 or more out of 15 evaluable subjects, the enrollment of second stage will be open and an additional of 15 evaluable subjects will be enrolled. Assuming the dropout rate is 10%, 45 subjects will be enrolled.

Phase II Part 2 is a expansion study and it is estimated to enroll 120 subjects to further assess the safety and efficacy of the investigational drug.

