#### Sample Size Determination

During phase I dose escalation study of MGD013 monotherapy, the starting dose of MGD013 will be 120 mg Q2W in one subject which has been enrolled in the group. The subsequent dose groups will adopt traditional 3+3 dose escalation scheme , with 3 - 6 evaluable subjects in each group; during dose escalation study of combination therapy, the traditional 3+3 dose escalation scheme will be used, and it is expected to have 30 - 43 subjects in total in Phase I.

There will be two cohorts in Phase II Part 1. Subjects who have previously received and not received immune checkpoint inhibitor treatment will be administered with MGD013 monotherapy or MGD013 in combination with brivanib alaninate. The SWOG two-stage design will be employed.

30 subjects are needed

There are two

stages in this part. In the first stage, if response (according to RECIST 1.1 criteria) is observed radiologically in 1 or more out of 15 evaluable subjects, the

enrollment of second stage will be open and an additional of 15 evaluable subjects will be enrolled.

40 subjects are needed

Similarly, there are 2 stages for the cohort. At least response of 3 out of 20 evaluable subjects at the first stage will support the decision to proceed to the second stage of subject accrual till there are 40 evaluable subjects in this cohort. Each cohort will have 70 evaluable subjects. Considering 10% dropout rate, up to 158 subjects will be enrolled.

According to safety and efficacy data of Phase II Part 1, a study treatment (MGD013 monotherapy or MGD013 in combination with brivanib alaninate) will be selected for Part 2 dose expansion in subjects who have previously received immune checkpoints inhibitor treatment. It is estimated to enroll 120 subjects for further assessment of its efficacy and safety.

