### Schematic diagram of the study:

Each cohort will enroll approximately 30 evaluable advanced HCC subjects who progressed after immune checkpoint inhibitor treatment, and approximately 40 evaluable advanced HCC subjects who have not previously received immune checkpoint inhibitor treatment. The SWOG two-stage design will be employed. In the first stage, 20 advanced HCC subjects who have not previously received immune checkpoint inhibitor treatment will be enrolled. If response is observed in 3 or more subjects (according to RECIST 1.1), the enrollment of second stage will be open and an additional of 20 evaluable subjects will be enrolled. The enrollment of advanced HCC subjects who have previously received immune checkpoint inhibitor treatment will be similar, there are 2 stages for the group and the response (according to RECIST 1.1) of 1 and more out of 15 evaluable subjects at the first stage will support the decision to proceed to the second stage of subject accrual until there are 30 evaluable subjects in this group. If the response in any treatment group is found less than the above standard in the first period, the enrollment of second stage will be terminated.

In Phase II study, 2 weeks (14 days) will be defined as a cycle, and subjects will continue to receive study treatment until disease progression (according to irRECIST), death or the occurrence of intolerable toxicity (whichever comes first). MGD013 will be administered for

at most 48 cycles. If subjects do not have disease progression after discontinuing MGD013, subjects of the combination therapy group may continue brivanib alaninate.

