Phase II Part 2 will expand the cohort study according to the safety and efficacy data obtained in Part 1. When at least 6 responders are observed among 30 evaluable patients (observed ORR=20%) in the post checkpoint inhibitor cohort in Part 1, the enrollment of Part 2 will be initiated. The treatment (MGD013 monotherapy or MGD013 in combination with Brivanib) that meets above criteria will proceed to Part 2. If both monotherapy and combination therapy achieve at least 6 responders in the post checkpoint inhibitor cohort, the decision of which treatment to proceed to Part 2 depends on the totality of safety and efficacy data from Part 1, and will be made by Safety Review Committee (SRC) after reviewing the data. About 120 advanced HCC subjects who have progressed following immune checkpoint inhibitor treatment will be enrolled to further assess the safety and efficacy of the study treatment. Decision on the study treatment (MGD013 monotherapy or in combination with brivanib alaninate) in Part 2 will be made by the sponsor according to the obtained data from Part 1.

The primary efficacy endpoint in Phase II study is BICR-assessed ORR according to RECIST1.1. Investigators will also evaluate objective anti-tumor efficacy and disease progression based on target lesions, non-target lesions and new lesions according to RECIST 1.1 and irRECIST criteria. The radiological responses that determine whether treatment groups in Part 1 will enter the second period after the completion of the first period of the study will be evaluated by investigators according to RECIST1.1. The subjects will be managed and evaluated for a disease progression that requires the discontinuation of the investigational drug by the investigators preferably according to irRECIST.

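### Section 9.2 gives 45 enrolled for the 15+15 cohort; at its own 10% dropout that cohort needs 34, and 45 is the figure for the 40-evaluable cohort

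*Combined protocol and SAP*

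**What the plan says.** Section 9.2 describes two two-stage cohorts for Phase II Part 1. The first has a 20-subject first stage and continues "subject accrual until there are 40 evaluable subjects in this cohort". A separate sentence, which names no cohort, comes next: "Assuming the dropout rate is 10%, 34 subjects will be enrolled". The second cohort opens its second stage, with 15 more evaluable subjects, once at least one of its first 15 has responded. The same paragraph then runs on without a break: "an additional of 15 evaluable subjects will be enrolled. Assuming the dropout rate is 10%, 45 subjects will be enrolled".

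Section 9.2 does not say which population each cohort is. Section 3.1.4 does: "Each cohort will enroll approximately 30 evaluable advanced HCC subjects who progressed after immune checkpoint inhibitor treatment, and approximately 40 evaluable advanced HCC subjects" without prior ICI. It assigns the 15-subject first stage to the post-ICI group and the 20-subject first stage to the ICI-naive group.

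The synopsis, under Sample Size Determination, takes the cohorts in the opposite order, with 15+15 first and then "Similarly, there are 2 stages for the cohort. At least response of 3 out of 20 evaluable subjects at the first stage". It gives no enrolled number for either cohort, only the total: "Each cohort will have 70 evaluable subjects. Considering 10% dropout rate, up to 158 subjects will be enrolled". In that sentence a cohort is a treatment (monotherapy or combination), each with 30 + 40 = 70 evaluable subjects.

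**The concern.** An enrolled number should follow from the evaluable target and the dropout rate stated beside it. For the 15+15 cohort it does not: 45 is half as many again as the 30 evaluable subjects required, which 10% dropout cannot explain.

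In the visible text, Section 9.2 is the only place that states enrolled numbers by cohort, and it gives no total to test them against. Adding the two figures does not expose the problem either, because 34 + 45 is the same whichever cohort each belongs to. Someone planning accrual from Section 9.2 would take the wrong number for the post-ICI cohort. That cohort decides whether Part 2 opens: "When at least 6 responders are observed among 30 evaluable patients (observed ORR=20%) in the post checkpoint inhibitor cohort in Part 1".

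**Working it through.** **Inputs**

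- 15+15 cohort: 15 + 15 = 30 evaluable (Section 9.2); post-ICI (Section 3.1.4).
- 20+20 cohort: 40 evaluable (Section 9.2); ICI-naive (Section 3.1.4).
- Dropout: 10% (Section 9.2 and synopsis).
- Enrolled figures printed in Section 9.2: 34 and 45.
- Part 1 total: up to 158 enrolled, 70 evaluable per treatment, two treatments (synopsis).

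**Step 1: try to reproduce the printed 45 for the 15+15 cohort.** With dropout rate d, the number to enrol is n/(1 − d), rounded up.

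- 30/0.9 = 33.3, so 34.
- The cruder rule n × (1 + d) gives 30 × 1.1 = 33.

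Neither gives 45. Enrolling 45 to obtain 30 would mean a dropout of 1 − 30/45 = 33.3%.

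**Step 2: find where 45 comes from.** For the other cohort, 40/0.9 = 44.4, so 45. The cruder rule gives 40 × 1.1 = 44.

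**Step 3: test the assignment against the synopsis total.**

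| Way of inflating | Part 1 total |
|---|---|
| Each cohort separately, n/0.9: 2 × (34 + 45) | 158 |
| Each treatment as a whole: 2 × (70/0.9 = 77.8, so 78) | 156 |
| All of Part 1 pooled: 140/0.9 = 155.6 | 156 |
| Each cohort separately, n × 1.1: 2 × (33 + 44) | 154 |

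Of these, only the first gives the stated 158. So 34 was derived from 30 evaluable and 45 from 40 evaluable.

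**Step 4: consider the 34.** There are two readings, because text appears to be missing around it.

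- If it belongs to the 40-evaluable cohort described just before it, it cannot be right: 34 enrolled cannot yield 40 evaluable. The two figures are then exchanged.
- If missing text had already turned to the 30-evaluable cohort, 34 is right. That cohort is then given both 34 and 45, and the 40-evaluable cohort has no enrolled figure in the visible text.

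On either reading, 45 is wrong where it stands.

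**Step 5: size.** 45 − 34 = 11 too many per treatment, and 2 × 11 = 22 over both treatments.

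**The case against.** The best counter-argument accepts the arithmetic and contests its reach.

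First, the exchange of both figures is not proven. The sentence with 34 stands alone and names no cohort. It comes directly before the description of the 15+15 cohort, and the surrounding text has gaps. This stands: only the misplacement of 45 can be asserted outright. The gaps do not help the 45, though, because nothing interrupts the 15+15 rule and the figure that follows it.

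Second, the post-ICI label is imported from Section 3.1.4. That is true, but Section 3.1.4 is explicit, and the arithmetic needs only 15 + 15 = 30.

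Third, the consequence is small. Accrual is defined by evaluable subjects (15 then 30, 20 then 40), the Part 2 trigger counts responders among 30 evaluable, and the synopsis caps Part 1 at 158. No error rate, power, decision rule or analysis set uses the enrolled counts, and nothing says they are limits. All of this is right. The 22 is therefore the size of the discrepancy in print, not a forecast of excess enrolment. It limits the importance of the point, but it does not make the stated number correct.

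**Conclusion.** The point holds. In Section 9.2 the 45 attached to the 15+15 cohort should be 34 under the section's own 10% dropout, and 45 is the number for the 40-evaluable cohort. This rests on the evaluable targets and dropout rate as printed, on rounding up n/(1 − d), and on the synopsis total of 158, which that rule reproduces exactly when applied to each cohort.

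That the 34 is also misplaced is likely but less certain. It fits the drafting order: the synopsis takes 15+15 first, Section 9.2 reverses this, and the figures still run 34 then 45.

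The effect is confined to the per-cohort enrolment figures. Over- or under-enrolment would follow only if those figures were applied literally as cohort limits.

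**What to change.** In Section 9.2, put the cohort's name beside each figure and state that the figures are per treatment:

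| Cohort (per treatment) | Stages | Evaluable | Enrolled at 10% dropout |
|---|---|---|---|
| Post-ICI | 15 + 15 | 30 | 34 |
| ICI-naive | 20 + 20 | 40 | 45 |
| Both cohorts | | 70 | 79 |

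Add the Part 1 total, 2 × 79 = 158, so that Section 9.2 can be checked against the synopsis. This is an editorial correction with no change to the total sample size, the stage rules or the analysis.

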## 9.3 Statistical Analysis Method

#### 9.3.1 Safety Analysis

Safety analysis is performed in the SS. Safety parameters include: physical examination, vital signs, AEs and laboratory tests, ECG, etc. AEs will be coded using MedDRA System Organ Class and Terminology.

The incidence rates and severity levels of adverse events, dose-limiting toxicity (DLT), adverse events leading to withdrawal from the study, adverse events leading to discontinuation, adverse events leading to death, and serious adverse events will be summarized. A line listing of AEs will be provided.

Each laboratory should examine the indicators and ECG, describe their changes during the study, use a cross-classification table to describe the normal and abnormal changes before and after treatment and provide a data list. Some specified parameters will be summarized descriptively per protocol.

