#### **Statistical Analysis Method**

#### Safety Analysis

Safety analysis is performed in the SS population. Safety parameters include physical examination, vital signs, AEs and laboratory tests, ECG, etc. AEs will be coded using the most updated MedDRA System Organ Class and Preferred Term.

The incidence and severity of AEs, dose-limiting toxicity (DLT, phase I study), AEs leading to withdrawal from study, AEs leading to drug discontinuation, AEs leading to death, and serious adverse events (SAEs)will be summarized.

For laboratory parameters and ECG, the change during the study will be summarized by descriptive analysis. The normal and abnormal laboratory values before and after treatment will be summarized using a shift table based on the lab normal range. Listing of data will be also provided. Some specified parameters will be summarized descriptively per protocol.

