## **Definition of evaluable subject**

An evaluable subject is defined as a subject who received  $\geq 75\%$  of pre-specified total dose of MGD013 and brivanib alaninate (combination treatment cohort) within the first two cycles (28 days) and has completed primary safety evaluation, **or** experiences DLT at any time within 28 days.

A cycle lasts for two weeks (14 days) in the study, and the first two cycles are the DLT evaluation period. Provided that 3 or 6 evaluable subjects in one dose group have completed the first two cycle evaluation and the dose escalation criteria is met, subsequent dose cohort is open to enroll. There will be no intra-subject dose escalations. Unevaluable subjects in Phase I will be replaced until at least 3 evaluable subjects are enrolled in each dose group. Approximately  $30 \sim 43$  evaluable subjects will be enrolled. The total number of subjects will depend upon the number of dose levels.

Subjects will continue treatment until disease progression, death or the occurrence of intolerable toxicity, whichever comes first. MGD013 will be used for at most 48 cycles. Subjects receiving combination therapy can continue using brivanib alaninate if there is still no disease progression after discontinuing MGD013.

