## **Definition of maximum tolerated dose (MTD)**

[figure not shown]
It is defined as the maximum dose at which <33% subjects suffer from DLTs; if 2 or more DLTs occur in a certain dose group, this dose is considered as intolerable, its prior dose level is defined as the maximum tolerated dose (MTD). There must be at least 6 evaluable subjects in the MTD dose group.

In Phase I dose escalation period, the **Safety Review Committee** (SRC) will decide whether to escalate to the next dose level or discontinue the escalation after reviewing the data from each dose group.

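### DLT incidence is placed in the safety set and no DLT-evaluable set is defined, so the reported rate is biased low in any dose group with both a DLT and a replaced subject

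*Combined protocol and SAP*

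**What the plan says.** **Reporting.** Section 9.3.1 begins "Safety analysis is performed in the SS". Its next paragraph says what will be summarised: "The incidence rates and severity levels of adverse events, dose-limiting toxicity (DLT), adverse events leading to withdrawal from the study", followed by further adverse event categories. It names no separate denominator for DLT. The synopsis also puts its safety analysis in the SS and lists DLT in the same way, marked as a Phase I item.

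**Analysis sets.** Section 9.1 gives the SS as follows: "SS: it includes subjects who have received at least one dose of the investigational drug and undergone safety assessment". It carries no evaluability condition. The only other sets defined there are the FAS and the PPS.

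**Dose decisions.** Section 3.1.1 defines an evaluable subject by two routes. One is receipt of at least 75% of the planned dose over the first two cycles (28 days) with the primary safety evaluation completed. The other is a DLT at any time in those 28 days. It adds: "Unevaluable subjects in Phase I will be replaced until at least 3 evaluable subjects are enrolled in each dose group". The escalation rules in Section 3.1.2 work on groups of 3 or 6 evaluable subjects. Section 3.1.3 says of the MTD: "It is defined as the maximum dose at which <33% subjects suffer from DLTs". The same sentence goes on to treat a dose as intolerable once 2 or more DLTs occur, and the MTD group must hold at least 6 evaluable subjects.

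**The concern.** The protocol decides on dose in one population and, read as written, reports DLT incidence in another. The difference runs in one direction only. Having a DLT is itself enough to be evaluable, so a subject replaced as unevaluable has no DLT by definition. If that subject was dosed and had a safety assessment, the subject enters the SS denominator and never the numerator. The SS rate can equal the evaluable rate or lie below it; it can never lie above.

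Safety and the RP2D are the Phase I primary objectives (Section 2.1.1), and the DLT table by dose level is where a reader will look to see why a dose was accepted or rejected. A percentage on a different base from the decision makes a dose look better tolerated than the evaluable data show.

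**Working it through.** **Inputs**
- Reporting set: SS, meaning one dose plus a safety assessment (Sections 9.1 and 9.3.1, synopsis).
- Decision base: evaluable subjects, 3 or 6 per group, at least 6 at the MTD (Sections 3.1.1 to 3.1.3).
- MTD rule: rate below 33%; 2 or more DLTs is intolerable (Section 3.1.3).
- Phase I unevaluable rate: not given in the documents.

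**Step 1: reproduce the protocol's rule.** The rate is DLTs divided by evaluable subjects. With 6 evaluable, 1/6 = 16.7% is below 33% and 2/6 = 33.3% is not. The rate rule and the count rule therefore agree on this base.

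**Step 2: put the same groups on the SS.** The rate becomes DLTs / (evaluable + replaced). For 6 evaluable subjects:

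| Replaced subjects | 1 DLT | 2 DLTs | 3 DLTs |
|---|---|---|---|
| 0 | 1/6 = 16.7% | 2/6 = 33.3% | 3/6 = 50.0% |
| 1 | 1/7 = 14.3% | 2/7 = 28.6% | 3/7 = 42.9% |
| 2 | 1/8 = 12.5% | 2/8 = 25.0% | 3/8 = 37.5% |
| 3 | 1/9 = 11.1% | 2/9 = 22.2% | 3/9 = 33.3% |
| 4 | 1/10 = 10.0% | 2/10 = 20.0% | 3/10 = 30.0% |

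**Step 3: when does the printed rate fall below 33% for a dose that is intolerable by count?** With 2 DLTs, once the SS group reaches 7: 6 evaluable plus 1 replaced, 5 plus 2, 4 plus 3, or 3 plus 4. With 3 DLTs in 6 evaluable, it takes 4 replaced subjects. With 1 DLT in 6 the percentage falls but no threshold is crossed.

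**Step 4: how likely is a replacement?** Let q be the chance that a subject is unevaluable, assumed independent between subjects. The chance of at least one replacement while accruing 6 evaluable subjects is 1 − (1 − q)^6.

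| Assumed q | Chance of at least one replacement |
|---|---|
| 5% | 1 − 0.95^6 = 26.5% |
| 10% | 1 − 0.90^6 = 46.9% |
| 15% | 1 − 0.85^6 = 62.3% |
| 20% | 1 − 0.80^6 = 73.8% |

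These values of q are illustrative. This is the chance of a replacement, not of a distorted rate; distortion also needs a DLT in the group and the replaced subject to qualify for the SS.

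**Step 5: is replacement plausible under this schedule?** MGD013 is given on Day 1 of each two-week cycle (Table 1), so the 28-day window holds two infusions. Missing one leaves 1/2 = 50% of the planned MGD013, under the 75% threshold. Section 8.4.1.2 has MGD013 withheld for some Grade 2 events, such as raised transaminases or nephritis, that the DLT list in Section 3.1.3 does not in general count. A subject who missed the second infusion for such a reason could be unevaluable, be replaced, and still sit in the SS as a treated subject without a DLT.

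**The case against.** **The count rule protects the decision.** A reader might infer that the SS denominator could let an intolerable dose pass as the MTD. The documents do not support that. The sentence in Section 3.1.3 that gives the 33% figure also makes 2 or more DLTs intolerable by count, Section 3.1.2 escalates on counts, and the Safety Review Committee reviews each dose group. Two DLTs are intolerable whether the table prints 2/6 or 2/8. This objection stands in full and confines the point to reporting.

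**The dilution is conditional.** With no replaced subject in a dose group, the two denominators coincide; with no DLT, the rate is zero on either. Two DLTs in a first cohort of 3 would need four replaced subjects before the SS rate fell below 33%. This also stands: the bias cannot be stated as certain, nor its size fixed in advance.

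**The SS denominator for DLT is read from a section-level sentence.** That is so. But the sentence governs the whole section, DLT is named within it, and no other denominator is offered. An analyst following the text would use the SS.

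**A SAP may settle it.** Section 9.3.2 refers to a SAP for details. Nothing in the documents supplied defines a DLT-evaluable set, and a SAP that followed Sections 9.1 and 9.3.1 literally would carry the fault over. If a separate SAP does define one, the protocol text still needs aligning with it.

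**Conclusion.** The point holds as a reporting fault that should be corrected. Sections 9.1 and 9.3.1 and the synopsis direct the DLT incidence summary to a set that can include subjects the dose decisions leave out. Where a dose group has at least one DLT and at least one dosed, safety-assessed, replaced subject, the reported rate is biased low. At the boundary that matters, one replaced subject moves 33.3% to 28.6% and two move it to 25.0%, so a dose declared intolerable could be shown with a rate under 33%.

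This rests on three things: the SS applying to DLT as Section 9.3.1 reads; the 33% figure being meant for evaluable subjects, which its sentence does not say but which is the base on which 2/6 matches the count rule; and an assumed number of replacements. It does not extend to any escalation, MTD or RP2D decision.

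**What to change.** - In Section 9.1 and the synopsis, add a DLT-evaluable set that uses the existing Section 3.1.1 definition of an evaluable subject.
- In Section 9.3.1, the synopsis and the SAP, state that DLT incidence by dose level is reported on that set and that all other safety summaries stay on the SS.
- List every replaced subject by dose level, with the reason for being unevaluable. Their adverse events remain visible in the SS tables.

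The cost is a few sentences and one extra listing. No dose, threshold, sample size or clinical rule changes. The one downside for the sponsor is that the reported DLT rate may be slightly less favourable than on the SS.
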